### Hypoglycemia

Severe hypoglycemia is a risk associated with the infusion of islets. Iatrogenic hypoglycemia in the immediate post-transplant period is a rare event. Frequent blood glucose monitoring immediately following islet transplantation is recommended to avoid severe unrecognized hypoglycemia in the early post-transplant period, In longer-term follow-up, life-threatening hypoglycemia (Grade 4) occurred in six of the 236 SAEs reported to CITR^131. For these six occurrences, the events occurred at the following time intervals; 59 days post the third infusion, 230 days post the second infusion, 296 days post the second infusion, 360 days post the third infusion, 673 days post third infusion, and 318 days post the second infusion. The local CITR investigators did not attribute any of the six events to the infusion procedure or to the immunosuppression medication..

#### **Hypotension**

Hypotension induced by infusion of islets into the portal vein is a rare complication of islet transplantation. Severe, grade 3 hypotension (*i.e.*, sustained hypotension persisting for more than 24 hrs requiring therapy) has not been experienced by any subject participating in a 36 subject international multicenter ITN islet trial, nor was it a recognized complication in 151 islet transplant procedures carried out consecutively at the University of Alberta. Frequent blood pressure monitoring in the post-transplant period is part of the protocol-regulated safety assessments.

In the era of non-purified islet preparations and high endotoxin collagenase preparations (before the availability of Liberase®), post-islet transplant hypotension requiring transient use of vasopressors was noted in 15% of the islet autograft recipients, of whom 50% required inotropic support with dopamine following injection until the end of surgery.

## **Disseminated Intravascular Coagulation (DIC)**

DIC has been documented after autologous islet transplantation of dispersed pancreatic islet tissue in 3 out of about 400 patients expected to have undergone this procedure .

Consumption of clotting factors from the extensive pancreatectomy surgery as well as the preparation of non-purified islet tissue from a chronic pancreatitis specimen may have contributed to the coagulopathy. DIC following islet allotransplantation has neither been reported in the literature nor communicated to the CITR. Frequent monitoring of coagulation parameters in the post-transplant period will be part of the protocol-regulated safety assessments.

#### **Hepatic Dysfunction and Steatosis**

Transient abnormalities in liver enzyme tests have been observed immediately following intraportal islet transplantation . Three of the 86 islet transplant recipients reported to CITR have experienced transient elevations of liver enzymes requiring prolongation of post-transplant hospitalization or admission . Persistence of laboratory abnormalities indicative of liver dysfunction and likely or definitely induced by intraportal islet transplantation is a rare event; abnormalities in liver function tests (LFTs) usually resolved within 4 weeks . No correlation between the increase in LFTs and graft characteristics or graft function was found. Periportal hepatic steatosis has been described following intraportal islet allotransplantation in 20% of the studied subjects  and appears to be due to a paracrine action of insulin secreted from intrahepatic islets. More subjects with steatosis required supplementary exogenous insulin than not , suggesting that steatosis may be associated with insulin resistance and graft dysfunction. The clinical relevance of steatosis associated with intrahepatic islet transplantation remains questionable. To the best of our knowledge, there is no evidence of clinically significant, persistent liver dysfunction following intraportal islet transplantation.

#### **Portal Hypertension**

Portal hypertension following intraportal infusion of unpurified allogeneic islet tissue resulted in a tear of the splenic capsule requiring splenectomy in one case. The elevation in portal pressure following intraportal islet transplantation is temporary in most instances. In 1981, Cameron *et al.* reported on 4 patients with chronic pancreatitis who developed portal hypertension during intraportal infusion of only partially purified auto islet preparations, and in whom direct or indirect measurements of portal pressure were performed 3 to 12 months later. In all patients, the portal pressure had returned to normal and portal venograms were normal. Casey *et al* reported on changes in portal pressure following sequential islet transplants at the University of Alberta, and found that third islet transplants were associated with significantly greater final portal pressures (18 mmHg) than first or second transplants (12 mmHg). The baseline pressures were normal in all cases, suggesting absence of chronic portal hypertension

#### **Portal Vein Thrombosis**

Transplanted islets release tissue factor and exhibit prothrombotic properties when infused to an intravascular site such as the portal vein 142. A partial portal vein thrombosis has been reported in one of six patients transplanted at the intramural National Institutes of Health (NIH) program 127. In the Edmonton single-center experience, the risk of partial vein thrombosis was 3% in more than 100 intraportal islet transplants 125. The management of partial vein thrombosis includes

anticoagulation therapy which may lead to intra-abdominal hemorrhage requiring transfusion and surgical intervention. There is one published report of complete thrombosis of the portal vein thrombosis after transplantation of partially purified pancreatic islets in a combined islet/liver allograft, which necessitated emergency re-transplantation of the liver. This complication probably related to the transplantation of partially purified islet tissue derived from 4 donors into a freshly transplanted liver. A right upper quadrant ultrasound including Doppler examination of the portal vein is performed on islet transplant recipients on days 1 and 7 post-transplant. Early diagnosis and prompt management of branch vein portal occlusion with systemic heparinization may prevent clot propagation. Repeated intraportal islet transplants are generally contraindicated in patients that have experienced prior portal thrombus.

#### **Injuries to Other Structures**

One instance of gall bladder perforation during percutaneous transhepatic catheterization of the portal vein requiring laparoscopic cholecystectomy has been reported to the Islet Transplant Registry. Acute cholecystitis, possibly related to percutaneous transhepatic catheterization of the portal vein, has been noted in 2 of the 86 islet allograft recipients reported to CITR^128. Gall bladder hematoma (n=1) and gall bladder opacification (n=2) have been observed as well.

#### 1.5.3.4 Follow-up Procedures

#### **Glomerular Filtration Rate (GFR)**

Risks associated with the GFR procedure are minimal and are related to the blood draw process. Rarely, the following will occur: excessive bleeding at blood draw site, syncope, extravasation of injection, hematoma, or infection. Iohexol has been widely used and has an excellent safety record. Very occasionally, allergic reactions to iohexol may occur.

#### 1.5.4 Benefits

Successful islet transplantation alleviates T1D patients from life-threatening hypoglycemia and psychosocially debilitating glycemic lability. While the long-term durability of these responses is at present uncertain, they persist for as long as some graft function is maintained, despite the eventual return to insulin therapy in the majority of recipients. This partial function, as indicated by continued c-peptide production, may be present in as many as 80% of recipients after 5 years. Furthermore, as long as graft function is maintained, fear of hypoglycemia and anxiety are significantly lower after islet transplantation. Indeed, T1D subjects in the DCCT who had persistent c-peptide production had a significantly reduced risk of severe hypoglycemia despite intensive insulin therapy. Additionally, while most transplant recipients experience only a temporary reprieve from exogenous insulin therapy, a few have maintained insulin-independent graft function for more than 3 years. Novel strategies aimed at promoting the engraftment or survival of transplanted islets may lead to improved long-term graft function and further the duration of insulin-independence after transplantation, and hopefully lead to reductions in the secondary complications of T1D.

#### 2. OBJECTIVES

#### 2.1 Primary Objective

The primary objective is to determine the proportion of subjects who are insulin independent at  $75 \pm 5$  days following the first islet transplant among subjects treated with an experimental islet transplant immunosuppression regimen which includes rituximab and excludes tacrolimus.

This group will be compared, as a secondary analysis, to subjects in a concurrent protocol, CIT-07, which uses a standard immunosuppressive regimen.

### 2.2 Secondary Objectives

The primary and secondary endpoints will be evaluated in this trial. Endpoints will be compared to corresponding endpoints in the CIT07 study.

In addition to achieving insulin independence, we hope to demonstrate that islet transplantation can result in near-normal glycemic control with amelioration from excessive glycemic lability and severe hypoglycemic episodes, and in an improved quality-of-life (QOL). Then the degree and durability of these responses will be determined.

Assessment for progression or development of secondary diabetes complications will include retinal photography, urinary albumin excretion (UAE), and GFR. Finally, we will monitor for procedural complications and AEs related to the immunosuppression regimen.

As previously mentioned, a drawback of the Edmonton approach is the use of CNI agents with known nephrotoxic and diabetogenic side effects. In fact, it's been recognized that some patients transplanted according to the "Edmonton protocol," who have early nephropathy, will experience a deterioration of renal function, mandating discontinuation of tacrolimus. Therefore, the large subset of T1D patients with early nephropathy are currently excluded from clinical islet transplantation trials due to the use of tacrolimus. In this regard, our pre-clinical results in NHP recipients (please see Preclinical Studies) have indicated that combined B- and T- lymphocyte immunotherapy (using a combination of rituximab and Thymoglobulin®), may obviate the need for tacrolimus maintenance therapy. Thus, we will determine the feasibility of a CNI free regimen in human islet transplantation by eliminating the tacrolimus used in the control arm (CIT-07) with the addition of rituximab during the initial induction of immunotherapy in the experimental arm (CIT-05). The benefit or harm of eliminating tacrolimus will be assessed by determining the proportion of subjects who remain insulin-independent at 365 days following the last islet transplant.

Further exploratory metabolic and immunologic studies will evaluate the mechanisms of graft function and dysfunction following islet transplantation. Metabolic studies will include:  $CGMS^{@}$ ; a frequently-sampled intravenous glucose tolerance (FSIGT) test that provides measures of first-phase insulin secretion (AIRglu), insulin sensitivity (SI), and their composite disposition index (DI); a glucose-potentiated arginine (GPA) test that provides estimates of functional  $\beta$ -cell mass (AIRarg and AIRmax [ $\beta$ -cell secretory capacity]); and paired hypoglycemic-euglycemic clamps that provide an evaluation of glucose counter-regulation. Immunologic

studies will include: evaluations of innate immunity; autoantibody responses; alloantibody responses; immunophenotyping and immunogenetic analysis of lymphocytes; and analysis of protective immunity and antigen-specific immune responses.

Together with other CIT data this will help to establish islet release criteria that accurately characterize the islet product and are predictive of transplant outcomes.

#### 3. STUDY DESIGN

This is an open-label, prospective, single-arm, single-center trial of islet transplantation under a novel experimental regimen that replaces the CNI tacrolimus with the anti-B lymphocyte agent rituximab. We will use rituximab at a dose of 375 mg/m² per injection administered twice, one week apart. This is a modification of the dose used for non-Hodgkin's lymphoma in humans, which is 375 mg/m² per injection administered four times at weekly intervals,  and is less than the recommended dose use for the treatment of rheumatoid arthritis, which is 1000 mg twice 15 days apart.  In addition, this dose lead to sustained (>6 months) B lymphocyte depletion, and caused a low (4.3%) incidence of human antichimeric antibody (HACA) formation . Previous studies demonstrated that this dose is safe and depletes B lymphocyte in patients with high-titer panel reactive antibodies experiencing kidney allograft rejection and awaiting kidney transplantation .

Objectives of this trial include gaining experience with the experimental immunosuppression treatment regimen as well as to determine the proportion of subjects with insulin independence on this experimental regimen. Should these subjects demonstrate a very high rate of insulin independence at  $75 \pm 5$  days post-transplant (a rate of 40% or higher would be considered high by current standards), then this treatment may be considered for further study.

There is a larger parallel trial with additional centers and more subjects (CIT-07) where subjects are treated with the standard Islet Transplant immunosuppression regimen. Subjects will be randomized to receive immunosuppression under either CIT-07 or this study (CIT-05) at the time a suitable islet preparation is available for transplantation. The randomization will provide a mechanism for balance between the two studies and to provide an objective selection of subjects to the two studies.

All subjects will be non-obese adults aged 18 – 65 years who have a more than 5 year history of T1D, absent stimulated c-peptide (<0.3 ng/mL), and either frequent moderate-to-severe hypoglycemic episodes or marked glycemic lability despite intensive insulin therapy and glucose monitoring under the direction of a diabetologist for at least 12 months. Additionally, all subjects will have a normal GFR and no macroalbuminuria while receiving ACE-inhibitors or angiotensin receptor antagonists in addition to other anti-hypertensive agents as needed in order to maintain their blood pressure <130/85 mmHg.

T1D islet transplant subjects will receive rituximab (375 mg/m² on days -2, and +6) and Thymoglobulin® (0.5 mg/kg on day -2, 1.0 mg/kg on day -1, and 1.5 mg/kg on days 0, 1, and 2 for a total of 6 mg/kg) for the induction of immunosuppression. One dose of methylprednisolone (2 mg/kg) will be administered with the Thymoglobulin® on day -2 to mitigate the transient cytokine-release associated with initial doses of Thymoglobulin® and rituximab. The first dose of rituximab will follow the first dose of Thymoglobulin®. Additional medications administered before each dose of Thymoglobulin® and rituximab include acetaminophen and diphenhydramine. During the immediate post-transplant period pentoxyfilline 400 mg po TID for 4 weeks will be administered as anti-inflammatory therapy. The maintenance regimen will include only sirolimus at a loading dose of 0.2 mg/kg of body weight on day -2, followed by 0.1 mg/kg per day adjusted to maintain a therapeutic trough level of 12 - 15 ng/mL.

Intraportal delivery of islets isolated from cadaveric donors will be achieved using a transperitoneal approach through a mini-laparotomy. Islets will be ABO compatible and have a negative serum crossmatch for T lymphocytes, but HLA matching will not be required. It is estimated that >600,000 IEq will be required per recipient at an average of 9,000 IEq/kg of recipient body weight to achieve insulin independence. To optimize the chance of achieving insulin-independence with no more than two procedures, islet preparations  $\geq$ 5,000 IEq/kg will be used for the first infusion, and islet preparations  $\geq$ 4,000 IE/kg will be used for subsequent infusions. The quantity of tissue transplanted will be < 7 mL per infusion. Quality control testing will include assessment of islet purity (> 30%), viability (> 70%), sterility (negative gram stain), and endotoxin content (< 5 IU/kg recipient) prior to release. Functional assessment of islets will also be performed.

Islets will be infused together with heparin and ciproflaxin (70 U/kg) with periodic portal pressure monitoring. Heparin will be continued for 48 hours after the procedure as an intravenous drip with target PPT levels of 50-60 seconds. Following completion of heparin, subjects will be treated with enoxaprin 30 mg subcutaneously bid through day 7.

Subjects who do not meet criteria for insulin-independence at any time after 75 days following the initial transplantation may be eligible for a second transplantation of islets. If the development of panel-reactive anti-HLA antibodies has occurred, only subjects with a PRA ≤ 20% will remain eligible, and both antibody specific and prior mismatched antigens will be avoided. To avoid problems related to Thymoglobulin® sensitization, we will administer daclizumab (2 mg/kg on day 0 followed every two weeks with 1 mg/kg for 4 additional doses) in order to sustain an anti-T lymphocyte induction effect. Should a third infusion of islets occur to achieve insulin-independence, only if the interval between the second and third islet infusions is >10 weeks will an additional course of daclizumab be administered. Rituximab administration will not be repeated with either a second or third infusion of islets.

The therapeutic trough level for sirolimus will be lowered to 10 - 12 ng/mL three months following the last islet infusion, or earlier if intolerable mouth ulcers or myelosuppression develops. If therapeutic trough levels of sirolimus cannot be maintained, mycophenolate mofetil (MMF, 500-1500 mg twice daily) may be added to ensure adequate immunosuppression: alternatively, sirolimus may be replaced by tacrolimus at a dose of 0.015 mg/kg PO BID adjusted to maintain trough levels of 6 - 10 ng/mL with the addition of mycophenolate mofetil (MMF, 500 - 1500 mg twice daily).

[figure not shown]

Figure 1: Study design diagram

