#### 1.4.4 Induction Immunosuppression for Subsequent Islet Transplants

The immunosuppressive regimen for subsequent islet transplants will be identical to the regimen for the initial islet transplant with the exception of Thymoglobulin®. Daclizumab or basiliximab will be used instead of Thymoglobulin® for all subsequent islet transplants.

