## **5.2.2** Subsequent Allogeneic Islet Transplants

The immunosuppressive regimen for subsequent islet transplants will be identical to the regimen for the initial islet transplant with the following exceptions.

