# 5.2.2.1.2 Basiliximab (Simulect®)

Two I.V. doses of basiliximab will be given with the first and second (if necessary) transplants. The first dose will be 20 mg and will be given within two hours prior to islet transplant on the day of islet transplantation. The second dose will be given on Day 4 after the transplant.

If a third transplant is deemed necessary and performed between 30 and 70 days after the second transplant, no additional doses of basiliximab will be given.

If a third islet transplant is deemed necessary and performed more than 70 days after the second transplant (see Section 7.5.1 for indications for subsequent transplants), both doses of basiliximab will be repeated.

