Hospital discharge is anticipated by Day +2, after which four weekly followed by four biweekly clinic visits will occur for the first 3 months to monitor glucose, electrolytes, creatinine, LFTs, CBC and differential, and trough levels of tacrolimus and rapamycin, and to titrate insulin therapy based on prior week's 4-7 daily BG measurements (pre- and 2-hours post-meals and bedtime). BG targets will be < 110 mg/dL fasting and < 140 mg/dL after meals for the first month, followed by < 126 mg/dL fasting and < 180 mg/dL after meals thereafter. Insulinindependence (defined in Section 3.1.1) will be determined at  $75 \pm 5$  days post-transplant based in part on the ability to achieve those latter glycemic targets.

Subjects who do not meet the criteria for insulin-independence at any time after 75 days following the initial transplantation will be eligible for a second (or third) transplantation of islets from one or more donor pancreata, unless sensitization to donor antigen, as indicated by the development of >20% panel-reactive anti-HLA antibodies, has occurred. A similar procedure for hospital admission will be followed for a subsequent infusion of islets, except that daclizumab will replace Thymoglobulin® and start on Day 0; thus, no period of islet culture will be required. Post-infusion care will be identical for the first 2 months.

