# 7.5.1 Criteria and Timing for Subsequent Islet Transplants

Islet transplant recipients who do not meet criteria for insulin independence (see section 3.1), but have either a basal or stimulated c-peptide level  $\geq 0.3$  ng/mL (0.1 nmol/L), will be considered **insulin-dependent with partial islet graft function**, and will be considered for a **second islet islet transplant**. Their insulin requirements will be determined by the total daily dose necessary to maintain the HbA1c  $\leq 7.0\%$ , the fasting capillary glucose level  $\leq 140$  mg/dL (7.8 mmol/L), and the 2-hour post-prandial capillary glucose levels  $\leq 180$  mg/dL (10.0 mmol/L), based on measuring capillary glucose levels a minimum of 21 times in a seven day period, and having at least one MAGE in that week.

In order to be eligible for a second islet transplant the following requirements must be met:

- 1. Subject received ≥5,000 IE/kg with the first transplant, but failed to achieve or maintain insulin independence
- 2. Subject has been compliant with study monitoring and prescribed immunosuppressive therapy
- 3. Subject has no unresolved SAEs
- 4. No evidence of progressive renal dysfunction, with blood creatinine rising above 2.0 mg/dL (177  $\mu$ mol/L)
- 5. No evidence of hypersensitization, allergic responses, or other potentially serious drug reactions to medications required by the protocol
- 6. PRA ≤50% by flow cytometry (assessment performed locally) and the alloantibody specificity not cross-reactive with antigen(s) present in the subsequent islet preparation in order to avoid unacceptable antigen(s).

A second islet transplant will be considered after the  $75 \pm 5$  days visit and metabolic assessment is completed, but before 8 months from the first transplant.

Islet transplant recipients who do not meet the criteria for insulin independence after the first infusion, and have both basal and stimulated c-peptide levels <0.3 ng/mL (0.1 nmol/L), will be considered for a second islet transplant only after review of the potency testing from the first transplant product and post-transplant clinical data by the Steering Committee that will have to give the final approval for the additional islet transplant.

If after the second islet transplant both basal and stimulated c-peptide levels remain <0.3 ng/mL (0.1 nmol/L), these recipients will be considered **failures** with no islet graft function, and immunosuppression will be withdrawn.

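### The re-transplant rules contradict each other on the PRA limit for eligibility and on whether rituximab is repeated

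*Protocol*

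**What the plan says.** **PRA limit.** Section 3, on subjects who have developed anti-HLA antibodies after the first transplant: "only subjects with a PRA ≤ 20% will remain eligible". Section 7.5 agrees. It makes subjects eligible for a second or third transplant unless sensitization, "as indicated by the development of >20% panel-reactive anti-HLA antibodies, has occurred". Section 7.5.1 sets a different limit: requirement 6 for a second transplant begins "PRA ≤50% by flow cytometry (assessment performed locally", and condition 10 for a third transplant is a PRA below 50.

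**Rituximab.** Section 3: "Rituximab administration will not be repeated with either a second or third infusion of islets". Section 1.4.4: "The immunosuppressive regimen for subsequent islet transplants will be identical to the regimen for the initial islet transplant with the exception of Thymoglobulin". Section 5.2.2, in the treatment chapter: "The immunosuppressive regimen for subsequent islet transplants will be identical to the regimen for the initial islet transplant with the following exceptions". The only exception then listed is the IL-2 receptor blocker (5.2.2.1, daclizumab or basiliximab). The initial regimen in Section 5.2.1.1 includes two rituximab doses.

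**Basiliximab (lesser point).** Section 5.2.2.1.2, under the heading for subsequent transplants: "Two I.V. doses of basiliximab will be given with the first and second (if necessary) transplants". The induction agent for the first transplant is Thymoglobulin (Synopsis; Sections 3 and 5.2.1.2).

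**The concern.** Two things cannot be read from the protocol without choosing between sections: who may be re-transplanted, and how much of the investigational drug a re-transplanted subject receives. Both feed reported results. Section 3.1.1 lists the proportions receiving a second and a third transplant, a full set of efficacy measures at days 75 and 365 after the final transplant, and the incidence of new anti-HLA antibodies. Section 2.2 says the benefit or harm of eliminating tacrolimus will be judged by insulin independence at 365 days after the last transplant. If subjects are handled differently according to the section consulted, these results mix different rules, and a reader cannot tell which regimen they describe. In a trial of 12, one subject handled differently moves a proportion by 1/12, about 8 percentage points.

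**Working it through.** No planned sample size, power or error rate is in dispute, so there is no stated figure to reproduce. The check compares the sections and then sizes the gap.

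**Step 1: PRA rules side by side**

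| Place | Second transplant | Third transplant |
|---|---|---|
| Section 3 | eligible at 20% or less | not stated separately |
| Section 7.5 | above 20% excludes | above 20% excludes |
| Section 7.5.1 | eligible at 50% or less | eligible below 50 |

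A subject above 20% and up to 50% is barred by Sections 3 and 7.5 but meets the PRA figure in Section 7.5.1. No section gives one of these limits precedence.

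**Step 2: rituximab text side by side**

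- Section 3: explicit, not repeated.
- Sections 1.4.4 and 5.2.2: identical regimen with listed exceptions. Rituximab is in the initial regimen and is not among the exceptions, so as written it is repeated.
- Synopsis, Treatment Description: rituximab with Thymoglobulin, an IL-2 receptor blocker standing in for Thymoglobulin later. It does not say whether rituximab drops out.
- Appendix 1: the schedule, with its rituximab PK and antibody (HACA) rows, restarts at each transplant. This does not settle dosing.

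**Step 3: size of the rituximab gap**

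Input: two doses of 375 mg/m² per course (Section 5.2.1.1), so 2 × 375 = 750 mg/m².

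| Transplants | Not repeated | Repeated |
|---|---|---|
| 1 | 2 doses, 750 mg/m² | 2 doses, 750 mg/m² |
| 2 | 2 doses, 750 mg/m² | 4 doses, 1500 mg/m² |
| 3 | 2 doses, 750 mg/m² | 6 doses, 2250 mg/m² |

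**Step 4: how many subjects the PRA conflict could touch**

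Inputs: n = 12 (Section 10.4); about 25% of islet-alone recipients with PRA above 20% on maintenance immunosuppression (Section 1.5.1.3). The protocol gives no expected insulin-independence rate *p*, so 20% to 80% is assumed. The 40% row is the rate the Synopsis would call high.

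Treating sensitization and insulin independence as unrelated:

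- expected number = 12 × (1 − *p*) × 0.25
- chance of at least one = 1 − [1 − 0.25(1 − *p*)]^12

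| Assumed *p* | Not insulin-independent, of 12 | Also PRA above 20% | Chance of at least one |
|---|---|---|---|
| 20% | 9.6 | 2.4 | 0.93 |
| 40% | 7.2 | 1.8 | 0.86 |
| 60% | 4.8 | 1.2 | 0.72 |
| 80% | 2.4 | 0.6 | 0.46 |

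Under that assumption these figures are upper bounds for the disputed band. Subjects above 50% are excluded under every rule, and the documents do not give their share. The other conditions in Section 7.5.1 remove more.

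**The case against.** **On rituximab, the text is not evenly balanced.** Section 5 opens by saying that dosage follows Section 3. Sections 1.4.2 and 2.2 place rituximab in the initial induction. Section 5.2.1.1 ties the first dose to the first ATG infusion, which does not occur at re-transplant, and Section 7.5 starts re-transplant induction on Day 0. A reader might infer two equally supported rules, or an intention to repeat. The documents do not support either: the weight leans towards Section 3, and the contrary reading comes from general sentences that do not name rituximab. What remains is that Section 5.2.2, where a treating team would look, offers a list of exceptions from which rituximab is absent.

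**On PRA, the conditions could be read as cumulative**, so that 20% always binds. The 50% limit would then never operate, and no section says the limits are to be combined this way.

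**On basiliximab**, the wording is most plausibly a slip, given the heading it sits under. It needs correcting but is not a rival regimen.

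**Timing.** A reader might infer a further conflict, because Sections 3 and 7.5 speak of any time after 75 days while Section 7.5.1 closes re-transplant at 8 months. The first phrase naturally describes when the insulin-independence criteria are not met. Section 7.5.1 adds a closing date, and the two are compatible.

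**Safety.** Section 1.5.2.3 cites a regulator's alert on two deaths after repeated rituximab courses. A reader might infer a demonstrated hazard of repeating it here. Those were lupus patients with prior cytotoxic drugs, and the section ends with an expert committee finding that the data do not support a causal relationship. The point rests on undefined exposure, not on shown harm.

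**Conclusion.** The contradictions on the PRA limit and on rituximab are real and stand in the current text. The PRA conflict is the firmer of the two. The rituximab conflict is one of wording, with the rest of the protocol leaning towards Section 3.

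In size, rituximab exposure is 2 versus 4 doses with two transplants. Six doses would need three transplants, so that figure does not apply to every re-transplanted subject. For PRA, about 0.6 to 2.4 of 12 subjects at most would be both sensitized and not insulin-independent. This rests on the assumed rates, on no association between the two events, and on a 25% frequency seen in earlier recipients rather than under a regimen meant to prevent anti-HLA antibodies. Section 1.5.1.3 reports that sensitization and graft failure go together, so the overlap could be larger than under independence. It could not exceed 25% of 12 = 3, and 3 should not be read as the expected number in dispute.

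A reader might also infer that the main result, or every final-transplant result, is compromised. It is not. The primary endpoint is fixed at day 75 after the first transplant, and Section 10.2.1 allows a later value only before any additional transplant. For a subject with one transplant, first and final coincide. The effect runs only through re-transplanted subjects, on secondary endpoints. The trial has one center, so the risk is inconsistent handling between subjects.

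**What to change.** Reconcile Sections 1.4.4, 3, 5.2.2, 5.2.2.1.2, 7.5 and 7.5.1 by amendment. State three rules once each: whether rituximab is given at a second or third transplant, the IL-2 receptor blocker rule by transplant number (Section 5.2.2), and the PRA limit for a second and for a third transplant (Section 7.5.1). Replace the competing text elsewhere with cross-references. Which rule applies is for the clinical team, and none is proposed here.

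The cost is a clarifying amendment, with no change to sample size or visits.
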